9.1.9. Overflow Subjects

The timing of immunogenicity blood draws for overflow subjects will be as follows:

- Any overflow subject who is challenged in a later cohort: blood draws at the time of challenge and 28 days after challenge.
- Any overflow subject who is not challenged: blood draws at 28 days post-vaccination, and again 28 days after the date they would have originally been challenged on.

Any overflow subject who is vaccinated but not challenged will be followed to the end of the study. Unsolicited AEs will be collected until 28 days after vaccination; SAEs will be collected until the end of the study.

Alternatively, these subjects can be challenged at the discretion of the sponsor, providing the study blind has not been broken.

9.2. Study Evaluations

9.2.1. Immunogenicity

Venous blood samples of approximately 10 mL and 50 mL will be collected for the determination of humoral and cellular responses, respectively, pre-vaccination, one or two days before viral challenge, and at 28 days post-challenge, or at the early exit visit if the subject prematurely terminates the study, without withdrawing consent.

All sample collection and processing will be performed by the staff at the clinical site according to current versions of approved standard operating procedures.

Humoral and cellular immunogenicity evaluations are summarized in [Table 5](#) and [Table 6](#), respectively.

Table 5: Summary of Immunogenicity Assays (Humoral)

Assay	Purpose
Exploratory endpoints	
RSV neutralization RSV-A Memphis 37b	Measure levels of the antibody to the challenge strain
Intranasal pre-F and post-F antibody*	Measure levels of vaccine induced antibody at the site of infection
RSV neutralization A2	Analysis of neutralizing antibodies to the A2 strain
RSV strain cross-neutralization	Analysis of cross-neutralizing antibodies to B and/or a different A strain
F-protein antibody (ELISA; pre- and/or post-fusion)	Analysis of antibodies binding to RSV F protein in post-fusion and/or pre-fusion form
RSV G/N ELISA	Analysis of binding antibodies to G and N proteins of RSV
Adenovirus neutralization assay	Analysis of neutralizing antibodies to adenovirus
Functional and molecular antibody characterization	Analysis of antibody characteristics including but not limited to ADCC, ADCP, avidity, Fc characteristics, Ig isotype

*From nasal wash samples, if the ELISA will be available

ADCC = antibody-dependent cell-mediated cytotoxicity; ADCP = antibody-dependent cellular phagocytosis; ELISA = enzyme-linked immunosorbent assay; F = fusion; Ig = immunoglobulin; RSV = respiratory syncytial virus

Table 6: Summary of Immunogenicity Assays (Cellular)

Assay	Purpose
Exploratory endpoints	
IFN γ ELISpot	T-cell IFN γ responses to RSV F-protein peptides
Flow cytometry (ICS)	Analysis of T-cell responses to RSV F-protein peptides (including, but not limited to, CD4/CD8, IL2, IFN γ , TNF α and/or activation markers, memory, Th1/Th2 subtyping)
Cytokine analysis	Analysis of secreted cytokines in RSV F peptide-stimulated PBMC supernatant, including, but not limited to, measurement of Th1/Th2 cytokine balance

ELISpot = enzyme-linked immunospot; F = fusion; ICS = intracellular cytokine staining; IFN γ = interferon gamma; IL = interleukin; PBMC = peripheral blood mononuclear cell; Th = T-helper (cell); RSV = respiratory syncytial virus; TNF α = tumor necrosis factor alpha

In addition to RT-PCR performed on nasal wash samples collected from Day 2 following challenge, any immunogenicity blood sample collected from a subject who subsequently undergoes challenge may also be assayed by a serological assay (eg, ELISA specific to RSV

protein G and/or N) to confirm RSV infection and evaluate the relationship between these assays and virological and clinical findings.

Nasal wash samples collected pre- and post-challenge and at discharge from the Unit will be used to assess any immunoglobulin or cellular immune component and its possible relation to viral load and clinical findings.

Instructions for the collection, handling, storage, and shipment of blood and nasal wash samples for immunogenicity assay are found in the Laboratory Manual that will be provided. Collection, handling, storage, and shipment of blood and nasal wash samples to the central laboratory must be under the specified, and where applicable, controlled temperature conditions as indicated in the Laboratory Manual.

9.2.2. Antiviral Activity Samples for Infectivity

Respiratory syncytial virus viral load will be measured in nasal washes (in both nostrils), using quantitative RT-PCR and a cell-based infectivity assay. Samples for the determination of RSV levels will be taken at several timepoints during the study, as indicated in the [Time and Events Schedule](#). The procedures for sample processing and storage will be provided in the hVIVO Analytical Plan. The changes in RSV viral load will not be reported as AEs or SAEs.

- RSV neutralization assay

To be eligible for the study a subject must be ‘sero-suitable’. Each subject will be initially screened for eligibility based on low immunity to the RSV-A Memphis 37b virus using a virus neutralization assay. This assay will be performed within 90 days of vaccination and on admission to the Unit (for post-hoc confirmation of RSV sero-susceptibility).

- Cell-based infectivity assay

Details will be provided in the Laboratory Manual.

- PCR for viral load: quantitative RT-PCR

The viral ribonucleic acid (RNA) will be extracted from the nasal wash, complementary deoxyribonucleic acid (cDNA) will be generated and quantitative RT-PCR of the N gene of the RSV strain will be performed. The quantitative RT-PCR will inform on the presence or absence of the RSV in the nasal wash and if the RSV is present the quantitative RT-PCR will provide the amount of virus (plaque forming unit equivalents [PFUe] per mL).

9.2.3. Mucus Weight and Tissue Count

At several timepoints during the study, as is indicated in the [Time and Events Schedule](#), the mucus weight (nasal) will be assessed.

Subjects will be given pre-weighed packets of paper tissues (handkerchiefs). After each tissue is used for nose blowing or sneezing, the subjects should store them in an airtight plastic bag.

Paper tissue and bag distribution first takes place on Study Day –1 at 08:00 a.m. (\pm 30 minutes). Paper tissue collection starts from Study Day 1 through the day of discharge at approximately the same time.

Subjects will be instructed to place used single tissues into a specified bag which will be collected the following morning. A daily 24-hour collection will take place and new bags will be distributed.

All paper tissues used by each subject will be collected for each 24-hour period throughout the quarantine phase, to determine daily mucus weight and number of tissues used.

Used and unused tissues will be counted. In case of missing tissues, they will be replaced by new dry tissues, and the subjects will be re-educated about proper tissue use and collection.

Collection time of the plastic bags, daily mucus weight, and number of tissues used should be recorded on the eCRF.

Tissues will not be stored after the mucus weight is determined.

9.2.4. RSV Subject Symptom Card

At several timepoints during the study, as indicated in the [Time and Events Schedule](#), all subjects will complete the SSC in order to assess the clinical symptoms of acute RSV infection (see [Attachment 3](#)).⁸ For each timepoint the results will be transcribed onto the eCRF by a member of the study-site personnel, and will be summarized according to the instructions.

The duration and severity of self-reported symptoms, clinical symptoms, respiratory tract illness, and systemic illnesses will be assessed and compared between treatment groups.

The investigator will review the subject's SSC entries on a daily basis after the administration of challenge virus. Subject symptom scores (self-assessment form), including body temperatures, and AEs will be conducted and daily during quarantine.

From challenge until discharge from the Unit, SSC findings greater than Grade 0 will be presumed to represent virus infection consequent to challenge, and will not additionally be captured as an AE, unless they meet the criteria for an SAE. The changes in RSV viral load will not be reported as AEs or SAEs.

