12.3. Procedures

12.3.1. All Adverse Events

Unsolicited AEs and special reporting situations will be reported from ICF signature until 28 days after vaccination, and from the entry into the Unit until 28 days after challenge.

From challenge until discharge from the Unit, SSC findings greater than Grade 0 will be presumed to represent virus infection consequent to challenge, and will not additionally be captured as an AE, unless they meet the criteria for an SAE. The changes in RSV viral load will not be reported as AEs or SAEs.

Solicited AEs will be recorded by each subject in the subject diary for 7 days after dosing. The investigator will review each subject's diary at the subsequent in-clinic visit; diary information will be transcribed by the study personnel in the on-site assessment forms in the eCRF.

The sponsor will evaluate any safety information that is spontaneously reported by an investigator beyond the time frame specified in the protocol.

The investigator will monitor and check the study data including all AE and any clinical laboratory data as they become available and will make determinations regarding the severity of the adverse experiences and their relation to study vaccine. All AEs will be deemed related to study vaccine or not related to study vaccine, or related to the viral challenge or not related to viral challenge, according to Section 12.1.2.

The investigator must review both post-injection reactogenicity and other AEs to insure the prompt and complete identification of all events that require expedited reporting as SAEs, invoke pausing rules or are other serious and unexpected events.

All AEs, regardless of seriousness, severity, or presumed relationship to study vaccine, must be recorded using medical terminology in the source document and the eCRF. Whenever possible, diagnoses should be given when signs and symptoms are due to a common etiology (eg, cough,

runny nose, sneezing, sore throat, and head congestion should be reported as “upper respiratory infection”). The investigator must record in the eCRF their opinion concerning the relationship of the AE to study vaccine. All measures required for AE management must be recorded in the source document and reported according to sponsor instructions.

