6.2. Secondary and Exploratory Efficacy Endpoints

The **secondary efficacy** endpoints are the following:

- Total clinical symptom score over time, with special interest to day 6 and 7. The total clinical symptom score is determined as the sum of the scores (grades) of the 13 self-reportable symptoms on the Subject Symptoms Card (SSC).

Note: ‘The symptom scores will be translated into numerical values as follows:

0 = ‘I have No symptom’

1 = ‘just noticeable’

2 = ‘It’s clearly bothersome from time to time, but it doesn’t stop me from participating in activities’

3 = ‘It’s quite bothersome most or all the time and it stops me from participating in activities’

4 = ‘Symptoms at rest’

- The viral load of RSV-A Memphis 37b as determined by quantitative RT-PCR assay of nasal wash samples over time, with special interest on Day 6 and Day 7 post challenge.
- The peak viral load is defined as the maximum viral load as determined by quantitative RT-PCR assay of nasal wash samples, observed over the whole quarantine period.
- The viral load of RSV-A Memphis 37b as determined by quantitative culture of RSV of nasal wash samples and the corresponding AUC, with special interest on Day 6 and Day 7 post challenge. The AUC will be calculated based on equation (1). In case the first timepoint after challenge and/ or last timepoint after challenge is missing, it will be set to zero. No other missing time point will be imputed.

The viral load values from the quantitative culture of RSV (plaque assay) range from 1.70 to 5.90 in log₁₀ PFU/ml. The following imputation rules will be used:

- <1.70 log₁₀ PFU/ml **not detected** -> 0
 - <1.70 log₁₀ PFU/ml **detected** -> 1.70
 - <2.70 log₁₀ PFU/ml **not detected** -> 0
 - <2.70 log₁₀ PFU/ml **detected** -> 2.70
 - >5.90 log₁₀ PFU/ml -> 6.00
 - INVALID -> missing
- Weight of mucus produced over time and the corresponding AUC. The AUC will be calculated based on equation (1). In case the first timepoint after challenge and/ or last time point after challenge is missing, it will be set to zero, no other missing time point will be imputed.
 - Number of tissues used per time point.

- Proportion of subjects with symptomatic RSV infection. Symptomatic RSV infection is defined in two ways:
 - Conservative: the subject has two or more quantifiable RT-PCR measurements on different samples and the subject has one of the following:

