 - symptoms from two different categories (Upper Respiratory, Lower Respiratory, Systemic) from the SSC, regardless of grade and assessment timepoint *OR*
 - any Grade 2 symptom from any category.
 - Liberal (RT-PCR): two or more quantifiable RT-PCR measurements plus any clinical symptom of any severity from the SSC.

The SSC categories are defined as follows:

- *Upper Respiratory symptoms*: runny nose, stuffy nose, sneezing, sore throat, earache
- *Lower Respiratory symptoms*: cough, shortness of breath, chest tightness, wheeze
- *Systemic symptoms*: malaise, headache, muscle and/or joint ache, chilliness/feverishness

Note: the quantifiable RT-PCR assessment and the symptoms should not necessarily occur at the same day.

The **exploratory efficacy** endpoints are the following:

- Proportion of subjects with symptomatic RSV infection based on RT-PCR or serology. Symptomatic RSV infection is defined as:
 - Liberal (RT-PCR or Serology): the subject has two or more quantifiable RT-PCR measurements or serology confirmation of RSV (4-fold increase in G a or G b Elisa, 28 days after challenge), and any clinical symptom of any severity.
- AUC of the total clinical symptom score. The AUC for the total clinical symptom score will be calculated based on equation (1). In case the first and/or last time point is missing, it will be set to zero, no other missing time point will be imputed.
- Clinical symptom scores per item over time
- Respiratory parameters measured by spirometry:
 - Forced expiratory volume in 1 second (%) – FEV1
 - Forced vital capacity (%) – FVC
 - FEV1/FVC Ratio (%) – FEV1/FVC

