6.2.1. Secondary and Exploratory Efficacy Endpoint Analysis

For viral loads of RSV-A Memphis 37b as determined by quantitative RT-PCR assay and by quantitative culture of RSV, number of observations, mean, standard error, median, first and third interquartile will be tabulated and means with standard errors will also be graphically presented per time point.

For clinical symptoms scores, total clinical symptom scores, mucus weight and number of tissues, number of observations, mean, standard error, median, first and third interquartile will be tabulated and means with standard errors will also be graphically presented per time point.

For peak viral load based on the quantitative RT-PCR assay, number of observations, mean, standard error, median, first and third interquartile will be tabulated for both groups and graphically presented with boxplots. Exact Wilcoxon Rank Sum tests will also be performed to compare the mean in the active versus placebo groups and the corresponding p-values will be presented. Note the study is only powered for the primary efficacy endpoint and not for any of the secondary one, interpreting these p-values should be done with caution.

For AUCs of viral loads, clinical symptoms and mucus weight, number of observations, mean, median, first and third interquartile (q1, q3) will be calculated for both groups and graphically presented with boxplots. Exact Wilcoxon Rank Sum tests will also be performed to compare AUCs in the active versus placebo groups and the corresponding p-values will be presented. Note the study is only powered for the primary efficacy endpoint and not for any of the secondary one, interpreting these p-values should be done with caution.

Descriptive statistics (number of observations, mean, standard errors, median, q1, q3) of values and changes from baseline for FEV₁, FVC, and FEV₁/FVC will be summarized at each scheduled timepoint. Mean with standard errors of actual values and changes from baseline will also be graphically presented. Finally, spirometry values that are below the clinically important limits, provided in the table below, will be classified as ‘abnormally low’ and the percentage of subjects with ‘abnormally low’ values will be summarized.

Parameter	Clinically Important Limits
FEV ₁	80%
FVC	80%
FEV ₁ /FVC	70%

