7.1.2. Analysis of Adverse Events

Number and percentage of subjects with at least one particular AE (unsolicited/solicited) will be tabulated. Unsolicited AEs will be summarized by System Organ Class and Preferred Term. Solicited AEs will be summarized by class (local, systemic) and preferred term.

For solicited AEs following tables will be provided: summary, by worst severity grade, grade 3, related (systemic only), time to onset (in days) and duration (in days) for most frequent events and body temperature. Note: For solicited events, duration is defined as number of days from the start of the event until resolution of the event. The time to first onset is defined as (date of first onset – reference date + 1). The reference date is the start date of the regimen period.

For unsolicited AEs following tables will be provided: summary table (including SAE, fatal outcome, AESI and discontinuation), all events, most frequent, grade 3, permanent stop of vaccine, related, SAE.

Listings and/or subject narratives will be provided as appropriate, for those subjects who die, discontinue study vaccinations due to an AE, or experience a severe or serious AE.

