7.3. Vital Signs and Physical Examination Findings

Similar to laboratory tests, only vital signs abnormalities emerging after vaccination and after challenge will be tabulated by worst abnormality grade.

Heart rate (beats per minutes, bpm), respiratory rate (breaths per minute), systolic blood pressure (mmHg) and diastolic blood pressure (mmHg) will be collected. The respective vital signs abnormalities are defined in Table 4. Moreover, only the vital signs values will be used, no clinical interpretations, therefore, grade 3 and 4 is shown combined as grade 4 always requires clinical interpretation.

Table 4: Vital Signs Toxicity

Vital Signs	Grade 1	Grade 2	Grade 3/4
Tachycardia – beats (HR) per minute	101 – 115	116 – 130	>130
Bradycardia – beats (HR) per minute	50 – 54	45 – 49	< 45
Hypertension (systolic) - mm Hg	141 – 150	151 – 155	>155
Hypertension (diastolic) - mm Hg	91 – 95	96 – 100	>100
Hypotension (systolic) - mm Hg	85 – 89	80 – 84	< 80
Respiratory Rate - breaths per minute	17-20	21-25	>25

Temperature from diary and on-site assessments from day of vaccination will be allocated to predefined temperature intervals (from 37.5° C until 40°C, in steps of half degree increments; eg <37.5, 37.5-<38, 38-<38.5, ... >40). A table will be created, showing the maximum temperature for both diary and onsite assessments combined.

A listing of temperatures from Day -2 or -1 will also be provided.

Temperature collected during the post challenge period will be summarized descriptively over each timepoint.

Finally, a listing of subjects with fever according to the FDA grading table, across the entire study period, will be provided.

Any abnormal physical examination result will be documented as AEs, by the investigator.

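### The SAP gives no by-arm count of subjects by worst symptom-card grade and no separate symptom duration, although Protocol 9.2.4 says both severity and duration will be compared

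*Protocol*

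**What the plan says.** Protocol 9.2.4 makes the commitment: "The duration and severity of self-reported symptoms, clinical symptoms, respiratory tract illness, and systemic illnesses will be assessed and compared between treatment groups".

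The next rule sits in Protocol 9.2.4 and again in 12.3.1: "From challenge until discharge from the Unit, SSC findings greater than Grade 0 will be presumed to represent virus infection consequent to challenge". The consequence for safety reporting follows in the same sentence, which says of these findings: "and will not additionally be captured as an AE, unless they meet the criteria for an SAE". A non-serious Grade 3 or 4 card finding in that period is therefore not an AE. On the SAP 6.2 scale, Grade 3 includes being "quite bothersome most or all the time and it stops me from participating in activities", and Grade 4 is symptoms at rest.

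For the card, SAP 6.2 and 6.2.1 plan:
- Item and total scores per time point. For clinical symptom scores, "total clinical symptom scores, mucus weight and number of tissues, number of observations, mean, standard error, median, first and third interquartile will be tabulated", with plots of means and standard errors.
- The AUC of the total score, with boxplots and an exact Wilcoxon test.
- Proportions meeting three symptomatic-infection definitions. These need RT-PCR or serology, and the highest grade named is "any Grade 2 symptom from any category".
- Individual profiles of the total score.
- Optionally, summaries repeated in infected and not-infected subjects.

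Elsewhere the SAP does tabulate by worst grade. For solicited AEs after vaccination, 7.1.2 lists tables "by worst severity grade, grade 3, related (systemic only), time to onset (in days) and duration (in days) for most frequent events". For vital signs, 7.3 says that "only vital signs abnormalities emerging after vaccination and after challenge will be tabulated by worst abnormality grade". Laboratory tests (7.2) and ECGs (7.4) are handled in a similar way.

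**The concern.** The protocol promises a comparison of two things, severity and duration, and closes the AE route for the data that would show them. The SAP then delivers severity only as averaged scores and gives duration no variable of its own. A reader of the report could not find out from any planned table how many subjects in each arm had severe symptoms after challenge, or how long symptoms lasted.

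Challenge is the planned, observed exposure to RSV after vaccination. Protocol 1.1 recalls that an earlier formalin-inactivated RSV vaccine was associated with enhanced respiratory disease in young children. If a vaccine prevents some infections while a few vaccinated subjects are more ill, average scores can favour the vaccine. A simple count by worst grade would keep the two effects apart.

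**Working it through.** The plan gives no figure to reproduce. The check has two parts: a reading of the planned outputs, and arithmetic on what they can show.

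**Planned card outputs against the two quantities named in Protocol 9.2.4**

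| SAP output | Subjects per arm at Grade 3 or 4? | Duration? |
|---|---|---|
| Item and total scores per time point (6.2.1) | No: means and quantiles | No |
| Total-score AUC, boxplot and Wilcoxon (6.2.1) | No | Only merged with severity |
| Infection proportions (6.2, 6.2.1) | No: no threshold above Grade 2, and PCR or serology needed | No |
| Individual total-score profiles (6.2.1) | No: single subjects, no count | Visible per subject, not summarised |
| Infected / not-infected summaries (6.2.1, optional) | No | No |
| Worst-grade and duration tables (7.1.2) | Solicited AEs after vaccination only | Solicited AEs only |

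**Quantiles.** Inputs: 22 subjects per arm (Protocol 11.2) and scores 0 to 4 (SAP 6.2). Put k subjects at Grade 4 on one item at one time point and the rest at 0. For k = 1 to 5, Q1, median and Q3 are all 0; Q3 rises above 0 from k = 6. The share at k = 5 is 5/22 = 23%. The mean does move: 4/22 = 0.18 (SE 0.18) for k = 1, 8/22 = 0.36 (SE 0.25) for k = 2, and 20/22 = 0.91 (SE 0.37) for k = 5.

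**AUC.** With flat profiles, Grade 3 for one day gives 3 × 24 = 72 score-hours, and Grade 1 for three days gives 1 × 72 = 72. The AUC cannot tell them apart.

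**Illustration with assumed scores.** Placebo: 14 of 22 infected, each with total score 6. Active: 7 of 22 infected, of whom 5 score 6 and 2 score 14 because they also have Grade 4 shortness of breath and Grade 4 wheeze (6 + 4 + 4).
- Placebo mean: 14 × 6 / 22 = 3.82.
- Active mean: (5 × 6 + 2 × 14) / 22 = 58/22 = 2.64, which is 31% lower.
- Median 0 v 6; Q3 6 v 6.
- If AUC is proportional to score, the exact Wilcoxon test with midranks gives a one-sided p of 0.064 in favour of the vaccine (0.034 with one severe subject, 0.089 with three).

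The same example in the other planned displays:
- AUC boxplot, on the score scale: the active box runs from 0 to 6 with upper fence 6 + 1.5 × 6 = 15, so the whisker reaches 14. The placebo maximum is 6.
- Per-item means: 0.36 v 0 for shortness of breath and for wheeze if both subjects peak on the same card. These are among 13 items × 36 cards (3 a day, Days 0 to 11) = 468 cells per arm, but they also appear in the item plots.
- Optional summary in infected subjects, if those are the 7 and the 14: 58/7 = 8.3 v 6.0, so the direction reverses.

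So the planned displays can raise the suspicion, but none of them states 2 v 0.

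**What a count could support.** For 22 v 22, one-sided Fisher: 2 v 0 gives p = 0.244, 4 v 0 gives 0.054, and 5 v 0 gives 0.024. With 0 of 22, the one-sided 95% upper bound is 1 − 0.05^(1/22) = 12.7%. The table can only be descriptive.

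**The case against.** The strongest reply is that severity is already compared. Item and total scores are tabulated and plotted, the symptom AUC is tested, and AUC reflects both severity and duration. In the illustration above, the AUC boxplot and the item plots would show something odd, and the infected-only summary would reverse the direction. That stands, except that the infected-only summary is worded as a possibility. It narrows the gap to a count of severe subjects and a separate duration.

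Serious illness also has other routes: SAEs, Grade 3 unsolicited AEs, pulmonary-function changes recorded as AEs (Protocol 9.2.5), low spirometry values, and worst-grade vital signs, laboratory tests and ECGs. A physician reviews the cards, and Protocol 17.9.2 provides for termination, after discussion, if any subject has severe or clinically significant illness from the challenge. These would catch some of what matters. None counts non-serious Grade 3 or 4 card findings by arm.

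Protocol 11.4 promises frequency tables for categorical variables, and the data presentation specifications, which are not available here, choose the tables. But the SAP turns card grades into numbers and defines neither a worst-grade nor a duration variable for the card, while section 1 says that the SAP holds all the information the analysis needs. Duration is also not a listed endpoint in Protocol 2.1.2, so the gap concerns a statement in 9.2.4 and not a missed endpoint.

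A reader might infer that the AE rule hides severe illness, or that vaccine-enhanced disease would go unseen. The documents do not support this. The rule avoids recording an efficacy measure twice. The enhanced disease cited was in young children given a different type of vaccine. Protocol 1.1 reports no histopathological sign of it with this vaccine in cotton rats, and 1.2 describes the model's symptoms as mild and mainly upper respiratory.

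**Conclusion.** The point holds in a limited form. Protocol 9.2.4 names severity and duration; the SAP delivers severity as averaged scores and AUC and does not analyse duration separately. No planned output says how many subjects per arm reached Grade 3 or 4 on the card. It would be too strong to say that severity goes uncompared or that severe illness would pass unnoticed.

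The size is small. No planned inference changes, and with 22 per arm a difference of 2 v 0 would not be persuasive by itself. The quantile result needs only the arm size. The 31% and p = 0.064 rest on invented scores and on AUC being proportional to score; they show what is possible, not what is expected. Two limits apply: the data presentation specifications were not available, and the sample card is redacted, so the grade wording comes from SAP 6.2.

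**What to change.** Add one descriptive by-arm table to SAP 6.2.1, on the ITTc set, covering challenge to discharge and regardless of PCR status. It should give:
- the number and percentage of subjects by worst symptom-card grade (0 to 4), overall and for the Upper Respiratory, Lower Respiratory and Systemic categories;
- the median and range of days with any symptom of Grade 1 or higher.

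The AE capture rules stay as they are. The cost is the programming of one table from card data already transcribed to the eCRF, with no new data, visits or unblinding. The downside is that small counts could be over-read, so the table should be labelled descriptive and carry no test.
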